2.2 Secondary Efficacy

- 2.21 To compare the surgical complication rates between oral SBI vs. placebo up to 1 month post-surgery (safety endpoint).
- 2.22 To compare the QOL, as derived from the previously-validated Symptom Distress Scale, the PQL (Postoperative Quality of Life questionnaire), and the uniscale (overall QOL item) between patients receiving oral SBI vs. placebo.
- 2.23 To compare the grade 2 or worse adverse event rates for patients receiving oral SBI vs. placebo.
- 2.24 To characterize the adverse event profile of oral SBI in postoperative gynecological cancer patients (safety endpoint).
- 2.25 To compare supplement adherence between patients receiving oral SBI vs. placebo.

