3.0 Patient Eligibility

3.1 Inclusion Criteria

- 3.11 Age \geq 18 years.
- 3.12 Diagnosis of gynecological cancer of any type or strong suspicion for cancer.
- 3.13 Patients must have begun postoperative oral intake of food prior to registration.
- 3.14 Open laparotomy or laparoscopic surgery undertaken with cancer therapeutic intent (not a subsequent surgery to manage a postoperative complication) that had occurred \leq 7 days prior to registration and that entailed more than a simple hysterectomy.
- 3.15 The following laboratory values obtained \leq 21 days prior to registration.
 - Creatinine \leq 1.5 x the upper limit of normal (ULN)
 - Absolute neutrophil count \geq 1500/mm³
 - Platelet count \geq 100,000/mm³
- 3.16 Ability to complete questionnaire(s) by themselves or with assistance.
- 3.17 Provide informed written consent.
- 3.18 Negative (serum) pregnancy test done \leq 7 days prior to randomization, for women of childbearing potential only.
- 3.19 Willing to provide mandatory baseline blood samples for correlative research purposes (see Section 6.12 and 14.0).

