5.0 Stratification Factors

- 5.1 Patient age: ≥ 65 years vs. < 65 years
- 5.2 Splenectomy and/or rectosigmoid resection: yes vs. no
- 5.3 Optimally debulked cancer (complete nodal and omental removal, as appropriate, with <1 cm of residual tumor, if appropriate): yes vs. no
- 5.4 Cancer type: ovarian vs. endometrial vs. other
- 5.5 Open laparotomy vs. laparoscopic surgery

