6.2 Randomization Procedures

6.21 The factors defined in Section 5.0 will be used as stratification factors.

6.22 After the patient has been registered into the study, the values of the stratification factors will be recorded, and the patient will be assigned to one of the following intervention groups using the Pocock and Simon dynamic allocation procedure which balances the marginal distributions of the stratification factors between the intervention groups [16].

- Oral Serum Bovine Immunoglobulin (SBI)
- Placebo

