16.0 Statistical Considerations and Methodology**16.1 Overview**

This randomized study is pilot in nature insofar as its main goal is to provide preliminary data to put in place the groundwork for a much larger, definitive study. The primary aim of the current study is to compare the time-to-quality of life (QOL) improvement from baseline in postoperative gynecological cancer patients who are receiving oral SBI vs. placebo. If this trial can provide preliminary evidence that oral SBI significantly improves the time-to-QOL improvement as compared to placebo, further study would be warranted to determine whether the administration of oral SBI shortens the time-to-chemotherapy administration post-operatively in ovarian cancer patients. In addition to time-to-QOL improvement, this trial will also compare adverse event rates, complication rates, QOL from validated QOL tools, and intervention compliance between patients receiving oral SBI vs. placebo.

- 16.11 **Primary Endpoint and Statistical Design:** To compare the time-to-QOL improvement from baseline in postoperative gynecological cancer patients who are receiving oral SBI vs. placebo.

Final Analysis:

The primary goal of this trial is to compare the oral SBI arm (experimental) to the placebo arm (standard), where the alternative hypothesis is that the experimental arm has a shorter time to QOL improvement from baseline as compared to the standard arm. For this primary endpoint, the total score of the 14-item Postoperative Quality of Life (PQL) tool [15] will be used, where the total score could range from 0 to 140 (0 being the worst and 140 being the best). These scores will be converted to the percentage scale, where a score of 140 will

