be converted to 100 and a score of 0 will remain as 0. This QOL will be measured weekly for the entire 12 week length of the study and at the end of the intervention. QOL improvement will be defined as at least a 10 point increase in the QOL score from baseline, on the percentage scale. This 10 point change represents a clinically meaningful improvement in QOL based on work done by Jeff Sloan [17]. The date at which the QOL score is first known to increase by at least 10 from baseline (on the 100 point scale), will be considered the event date for the purpose of analysis. Patients without at least a 10 point increase in QOL from baseline, will be censored on their last QOL evaluation date up to a maximum of 12 weeks. We will enter a total of 70 evaluable patients (35 per arm) using a 1:1 randomization scheme. The primary analysis will be a comparison of oral SBI vs. placebo using a two-sided log-rank test between the 2 Kaplan-Meier curves [18]. This analysis will take place after an approximate 16 month accrual period, and after 66 total events across both arms combined (which should happen after about 12 weeks of follow-up in all evaluable patients). Additionally, we assume a constant accrual rate over the course of the study, and that no patients will drop-out of the study, since historically the lost to follow-up rate is <1%. To determine the appropriate sample size of 35 evaluable patients per arm, we assumed exponential survival and that the median time-to-QOL improvement is around 3 weeks in the oral SBI arm and 6 weeks in the placebo arm (HR=2). This hazard ratio is based on our institution's data which shows that patients often begin postoperative chemotherapy 6 weeks after surgery. These assumptions yield 80% power to detect a significant difference between the arms using a 2-sided log-rank test at alpha=0.05. All patients who meet the eligibility criteria, sign the consent form, and are randomized, will be considered evaluable for this endpoint. All eligible patients will be followed a maximum of 12 weeks. If the 2-sided log-rank test p-value is < 0.05 showing significantly shortened time-to-QOL improvement in the oral SBI arm as compared to placebo, further study will be warranted. Of course, any final decisions will be based on all primary and secondary endpoints.

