16.62 **Intervention Compliance:** Intervention compliance will be assessed using the Compliance Questionnaire in Appendix V. The frequency and percentage for each Compliance Questionnaire category will be summarized descriptively by cycle and by intervention arm. In addition, cycle by cycle compliance data will be compared between the 2 arms using a Chi-square test.

16.63 **Quality of Life:** QOL will be measured with 3 QOL tools. For the primary endpoint, the total score from the 14-item Postoperative Quality of Life (PQL) tool [15] (Appendix II) will be used (16.11). As a secondary analysis, all 14 of the individual items from the PQL tool (Appendix II), along with the 4 additional items after the PQL questions (Appendix II) will be analyzed and compared between the 2 intervention arms. In addition, the time-to-QOL improvement will be compared between the 2 arms for any increase (> 0) from baseline for the total score from the PQL tool. This will be done descriptively, and using a Kaplan-Meier analysis [18], where any increase in the QOL from baseline will represent an event. QOL will also be measured using the Uniscale (Appendix III), and the previously-validated Symptom Distress Scale (SDS; Appendix IV). These QOL tools will measure QOL at baseline, every week up to 12 weeks post-randomization, and at the end of intervention. Differences between post-randomization and baseline QOL scores will be analyzed and compared between the 2 arms using a Wilcoxon Rank-sum test. Also, other graphical and statistical methods will be used to compare the QOL and time-to-QOL improvement between the 2 arms. As an exploratory analysis, we will also collect QOL data on patients who do not start intervention/placebo or discontinue intervention/placebo early and are willing to be followed per the test schedule (Section 4). This analysis will be descriptive in nature to see if these patients have a poorer QOL than patients who stay on study.

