16.64 **Translational Component:** The hypothesis is that oral SBI will improve postoperative recovery. However, we know of no biomarkers indicative of postoperative recovery. Hence in an exploratory manner, we will measure a host of candidate biomarkers. This study will include serial assessment at baseline, at a mid-way timepoint, and at the end of the intervention intervention. The differences between biomarker values over time will be compared between the 2 intervention arms using a Wilcoxon Rank-sum test. In addition, other graphical and statistical methods will be used to compare the data over time between oral SBI and placebo. All these analyses will be considered hypothesis-generating.

16.7 **Inclusion of Women and Minorities**

16.71 This study will be available to all eligible patients, regardless of race, or ethnic origin.

16.72 There is no information currently available regarding differential effects of this regimen in subsets defined by race, or ethnicity, and there is no reason to expect such differences to exist. Therefore, although the planned analysis will, as

always, look for differences in intervention effect based on racial groupings, the sample size is not increased in order to provide additional power for subset analyses.

16.73 The geographical region served by the Mayo Clinic has a population which includes approximately 5% minorities. We expect about 5% of patients will be classified as minorities by race and all will be women. Expected sizes of racial subsets are shown in the following table:

Accrual Estimates by Ethnicity/Race

Ethnic Category	Sex/Gender			
	Females	Males	Unknown	Total
Hispanic or Latino	0	0	0	0
Not Hispanic or Latino	100	0	0	100
Ethnic Category: Total of all subjects	100	0	0	100
Racial Category				
American Indian or Alaskan Native	0	0	0	0
Asian	2	0	0	2
Black or African American	3	0	0	3
Native Hawaiian or other Pacific Islander	0	0	0	0
White	95	0	0	95
Racial Category: Total of all subjects	100	0	0	100

Ethnic Categories: **Hispanic or Latino** – a person of Cuban, Mexican, Puerto Rican, South or Central American, or other Spanish culture or origin, regardless of race. The term “Spanish origin” can also be used in addition to “Hispanic or Latino.”

- **Not Hispanic or Latino**

Racial Categories: **American Indian or Alaskan Native** – a person having origins in any of the original peoples of North, Central, or South America, and who maintains tribal affiliations or community attachment.

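### Secondary quality-of-life scores are compared as change from baseline with no baseline covariate: a valid test, but generally less precise than adjusting for baseline

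*Combined protocol and SAP*

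**What the plan says.** Goal 2.22 in section 2.2 is a between-arm QOL comparison on three tools: "To compare the QOL, as derived from the previously-validated Symptom Distress Scale, the PQL (Postoperative Quality of Life questionnaire), and the uniscale". Section 16.63 collects these scores at baseline, weekly to week 12 and at the end of the intervention, and gives the test: "Differences between post-randomization and baseline QOL scores will be analyzed and compared between the 2 arms using a Wilcoxon Rank-sum test". It does not say which post-randomization week, or which summary of the weeks, supplies the difference. It then allows for further graphical and statistical methods without naming any. No regression, ANCOVA or mixed model, and no baseline covariate, appears in section 16.

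Two statements show how the result will be used. Section 16.1 says of the trial that "its main goal is to provide preliminary data to put in place the groundwork for a much larger, definitive study". Section 16.11, after making the primary log-rank p-value the trigger for further study, adds: "Of course, any final decisions will be based on all primary and secondary endpoints".

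**The concern.** Using baseline by subtraction and using it as a covariate are not equivalent. Subtraction assumes that each point of baseline carries over into one full point of follow-up. If the carry-over is weaker, subtraction adds baseline noise to the comparison. If it is weak enough, the change score is less precise than follow-up scores analysed with no regard to baseline.

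A weak carry-over is plausible here, though not known. Section 3.14 requires surgery at most "7 days prior to registration and that entailed more than a simple hysterectomy", so baseline is taken early in recovery, while follow-up runs to week 12. With 35 evaluable patients per arm there is little precision to spare. The secondary QOL results are to inform the decision on further work, and a less precise comparison is weaker evidence for it.

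**Working it through.** The plan states no power or precision figure for the secondary QOL comparison, so there is no figure of its own to reproduce.

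**Inputs.** From section 16.11: 35 evaluable patients per arm, 1:1. Borrowed from the primary test: two-sided 0.05. Assumed, because the documents give neither: the correlation rho between baseline and follow-up score, and k = follow-up SD / baseline SD. The effect size (0.6 of the follow-up SD) is also assumed.

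**Formulas.** With the baseline SD set to 1, the per-patient variances are:
- change score: 1 + k² − 2·rho·k
- follow-up score adjusted for baseline: k²(1 − rho²)
- follow-up score alone: k²

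The first minus the second is (1 − rho·k)². This is never negative and is zero only when rho·k = 1, so in large samples linear adjustment is never less precise than subtraction. The first exceeds the third when rho < 1/(2k); below that point, subtraction is worse than ignoring baseline.

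**Variance ratio, change score over adjusted** = (1 + k² − 2·rho·k) / (k²(1 − rho²)):

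| k | rho 0.3 | rho 0.5 | rho 0.7 | worse than ignoring baseline if |
|---|---|---|---|---|
| 0.8 | 1.99 | 1.75 | 1.59 | rho < 0.625 |
| 1 | 1.54 | 1.33 | 1.18 | rho < 0.5 |
| 1.25 | 1.27 | 1.12 | 1.02 | rho < 0.4 |

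Example, k = 1 and rho = 0.5: (1 + 1 − 1) / (1 − 0.25) = 1.33. With k = 1 the ratio reduces to 2/(1 + rho), which is 1.05 at rho 0.9.

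**In patients.** Dividing 35 by the ratio gives the number per arm that would yield the same precision with baseline as a covariate. For k = 1 this is about 23, 26 and 30 at rho 0.3, 0.5 and 0.7. At rho 0.5 it is 20 for k = 0.8 and 31 for k = 1.25.

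**In confidence intervals.** For k = 1, the 95% half-width at rho 0.3, 0.5 and 0.7 is 0.56, 0.48 and 0.37 SD for the change score, against 0.46, 0.41 and 0.34 SD adjusted.

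**In power.** Simulated with normal scores, one follow-up week, complete data, 35 per arm and an effect of 0.6 SD:

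| Setting | Wilcoxon on change | Baseline as covariate |
|---|---|---|
| k = 1, rho 0.3 | 52–54% | 73% |
| k = 1, rho 0.5 | 67–68% | 81–82% |
| k = 1, rho 0.7 | 88% | 93% |
| k = 1.25, rho 0.7 | about 91% | 92–93% |

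The ranges are the spread over repeated simulations. At k = 1 and rho 0.3, a Wilcoxon test on follow-up alone reaches 67 to 68%, above the change score, as the formula predicts.

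For k = 0.8 and rho 0.7, a normal approximation with Wilcoxon efficiency 0.955 gives the following. The effect is 0.6 × 0.8 = 0.48.
- Change score: SE = √((2/35) × 0.52/0.955) = 0.176. 0.48/0.176 − 1.96 = 0.76, so power is about 78%.
- Adjusted: SE = √((2/35) × 0.3264) = 0.137. 0.48/0.137 − 1.96 = 1.55, so power is about 94%.

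**Validity.** With no effect, both tests rejected in about 5% of simulated trials.

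**The case against.** The strongest reply is that the size is unknown. The often-quoted ratio 2/(1 + rho), and the rule that subtraction loses unless the correlation is very high, hold only for equal SDs. If scores spread out during follow-up, rho·k can be near 1 at an ordinary correlation and the loss disappears. This stands, and it is why the results above are given over both rho and k. It does not reverse the direction, because the loss is (1 − rho·k)².

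A second reply is that bounded, ordinal scores suit a rank test, and that Wilcoxon on change is simple and valid. Validity is conceded. The precision argument survives on less convenient scores. At rho 0.3, 0.5 and 0.7, power for PQL-like scores (0 to 100, assumed means 50 and 70, SD 18) was 49, 62 and 82% against 72, 80 and 92%. For Uniscale-like integers (0 to 10, assumed means 5 and 7, SD 2) it was 46, 58 and 78% against 70, 77 and 89%. A rank-based adjusted analysis, however, is not uniformly better than the planned test. For k = 1, rho 0.9 and a 0.4 SD effect it reached 93% against 95% for Wilcoxon on change. For k = 1.25, rho 0.7 and 0.6 SD it reached about 90% against 91 to 92%.

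Third, the plan is not confined to a p-value. Section 16.63 leaves room for other methods, and the weekly scores are collected, so SDs and correlations for a later trial can still be obtained. That is right: no data are lost. What is missing is commitment in advance to an adjusted comparison.

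A reader might also infer that the primary log-rank test loses power because it uses neither baseline nor the five allocation factors of section 5.0. The documents do not support this. They give no prognostic strength for those factors, and the unadjusted log-rank test is valid. Nor does the point need extending to the biomarkers: section 16.64 has a similar change-score test but already labels those analyses hypothesis-generating.

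**Conclusion.** The point holds as one of precision. The planned Wilcoxon test on change is valid but generally less precise than an analysis with baseline QOL as a covariate, and none is pre-specified. Over the assumed range (rho 0.3 to 0.7, k 0.8 to 1.25) the variance penalty runs from 1.99 down to 1.02. With equal SDs and a 0.6 SD effect it costs about 20, 14 and 5 points of power at rho 0.3, 0.5 and 0.7. These figures rest on assumed correlations and SDs, and on one follow-up week with complete, normal data; a comparison of 12-week means was not simulated.

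It would go too far to say that the QOL comparison is biased, or that a large loss is certain. Error rates are intact, and the loss is negligible where rho·k is near 1. The endpoints are secondary, the trial is a pilot, and the explicit trigger for further study is the primary test. The change is worth considering because it costs almost nothing.

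**What to change.** In section 16.63, for the PQL total, Uniscale and SDS, make the main secondary comparison an analysis of the follow-up score on arm with the baseline score as covariate. Fix the contrast in advance: either one named week (ANCOVA) or the mean over the 12 weeks. Report the adjusted difference with its 95% CI. Keep the planned Wilcoxon test on change as a sensitivity analysis.

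The cost is SAP wording, a little programming, one degree of freedom and an assumption of linearity in baseline. No extra patients or visits are needed. If a rank-based adjusted version is preferred for the bounded scores, expect it to give up about 2 to 3 points of power against the linear one at 0.6 SD. It can fall slightly below the Wilcoxon on change when the correlation is about 0.9, or more generally when rho·k is close to 1.

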17.0 Pathology Considerations/Tissue Biospecimens: None

18.0 Records and Data Collection Procedures

18.1 Submission Timetable

18.11 Initial Material(s)

CRF	Active-Monitoring Phase (Compliance with Test Schedule Section 4.0)
On-Study Form	
Baseline Adverse Event Form	
Research Blood Submission Form - Baseline (see Section 14.0)	≤2 weeks after registration
End of Active Intervention/Cancel Notification Form	Submit ≤2 weeks after registration if withdrawal/refusal occurs prior to beginning protocol therapy
Patient Questionnaire - Baseline Booklet	≤2 weeks after registration - Patient questionnaire booklet must be used; copies are not acceptable for this submission.
Patient Questionnaire Booklet Compliance Form	≤2 weeks after registration - This form must be completed only if the Patient Questionnaire – Baseline booklet contains absolutely NO patient provided assessment information.

18.12 Test Schedule Material(s)

CRF	Active-Monitoring Phase (Compliance with Test Schedule Section 4.0)		
	At each evaluation during the intervention period	At end of intervention	Observation/Crossover
Nurse/CRA Evaluation/Intervention Form	X	X	
Nurse/CRA Observation Form (4 weeks after completion of intervention)			X
Adverse Event Form	X	X	X*
Research Blood Submission Form	X (see Section 14.0)		
Patient Questionnaire	X ¹	X ¹	X
Patient Questionnaire Booklet Compliance Form	X ²	X ²	
End of Active Intervention/Cancel Notification Form		X	
Notification Form – Grade 4 or 5 Non- AER Reportable Events/Hospitalization Form	At each occurrence (see Section 10.0)		
ADR/AER	At each occurrence (see Section 10.0)		

* If the patient does not start therapy, adverse events will not be collected.

1. Patient questionnaire booklet **must** be used; copies are not acceptable for this submission.

2. This form must be completed **only** if the Patient Questionnaire contains absolutely **NO** patient provided assessment information.

19.0 Budget

- 19.1 Costs charged to patient: routine clinical care
- 19.2 Tests to be research funded: Research samples.
- 19.3 Other budget concerns: None

Appendix II Postoperative Quality of Life Questionnaire

Name and
Patient number _____ **Date** _____

The following questions are designed to gauge your current quality of life. Circle the answer that best indicates how you feel.

1. Quality of Life (0 = worst; 10 = best)

0 1 2 3 4 5 6 7 8 9 10

2. Quality of Health (0 = worst; 10 = best)

0 1 2 3 4 5 6 7 8 9 10

3. Level of Energy (0 = worst; 10 = best)

0 1 2 3 4 5 6 7 8 9 10

4. Pain at Rest

No Pain										Worst pain
0	1	2	3	4	5	6	7	8	9	10

5. Pain at Current Maximum Level of Activity

No Pain										Worst pain
0	1	2	3	4	5	6	7	8	9	10

6. Severity of Nausea or Vomiting

No nausea or vomiting										Worst nausea or vomiting
0	1	2	3	4	5	6	7	8	9	10

7. Fatigue

No Fatigue										Worst fatigue
0	1	2	3	4	5	6	7	8	9	10

8. How close is your bowel function to normal? (0 = most abnormal; 10 = normal)

0 1 2 3 4 5 6 7 8 9 10

9. How close are you to overall normal functioning for you? (0 = most abnormal; 10 = normal)

0 1 2 3 4 5 6 7 8 9 10

10. How close are you to your normal ability to get around the house? (0 = most abnormal; 10 = normal)

0 1 2 3 4 5 6 7 8 9 10

11. How close are you to your usual level of leisure activity? (0 = most abnormal; 10 = normal)

0 1 2 3 4 5 6 7 8 9 10

12. At what level is your sexual activity compared with normal? (0 = most abnormal; 10 = normal)

0 1 2 3 4 5 6 7 8 9 10

13. What is your current level of happiness: (0=sad; 10=happy)

0 1 2 3 4 5 6 7 8 9 10

14. What is your satisfaction with your overall level of medical care, including and since any surgery? (0=dissatisfied; 10=100% satisfied)

0 1 2 3 4 5 6 7 8 9 10

Additional Questions related to Quality of Life Post-surgery

1. Level of sleepiness

Totally alert	Very sleepy
0 1 2 3 4 5 6 7 8 9 10	

2. How many times per day on average did you experience nausea or vomiting?

Never 1-2 times 3-5 times > 5 times

3. How many times per day on average did you have a bowel movement

None 1 time 2-3 times 3-5 times > 5 times

Type 6		Fluffy pieces with ragged edges, a mushy stool
--------	--	--

Type 7		Watery, no solid pieces. Entirely Liquid
--------	--	--

4. What picture represents the typical bowel movement you had over the past 7 days. Please place an “X” over the appropriate picture.

Bristol Stool Chart

Type 1		Separate hard lumps, like nuts (hard to pass)
Type 2		Sausage-shaped but lumpy
Type 3		Like a sausage but with cracks on the surface
Type 4		Like a sausage or snake, smooth and soft
Type 5		Soft blobs with clear-cut edges
Type 6		Fluffy pieces with ragged edges, a mushy stool
Type 7		Watery, no solid pieces. Entirely Liquid

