15.14 **Administration:** SBI is administered orally or enterally. Each patient will be instructed to add the contents of one packet (5 grams) to a cup and dissolve the powder with approximately on-half cup (4 fl. ounces or 120 mL) of water. The patient will stir to mix and drink the contents. The patient will take one dose twice a day, in the morning and the evening, with or without food. Foods such as applesauce or pudding may be used instead of liquid to blend the product if the patient desires.

15.15 **Potential Agent Interactions:** No significant interactions of SBI with commonly prescribed medications have been observed.

15.16 **Known potential toxicities:** Study subjects with known beef allergies or allergies to other components of SBI should not take SBI. As with any ingested food or product, subjects who develop a hypersensitivity or food intolerance to SBI should discontinue its use. Subjects who are pregnant or breastfeeding should not take SBI, as there are no data regarding the effects. Serum-derived bovine immunoglobulin has self-affirmed generally recognized as safe (GRAS) status, with no objections from the FDA, and is demonstrated to be safe and well tolerated in pediatric and adult patients. SBI is marketed in Mexico, the Czech Republic, Japan, Egypt, and the United States. More than 100,000 kg of SBI in various dosages have been ingested by the general population since 2001. No serious adverse events have been reported to the manufacturer or the FDA. Literature reports indicate AEs include worsening or reoccurrence of diarrhea, constipation, and worsening neuropathy. Increased urination, stomach cramps, fatigue, headache, sore throat, softened stools, and nausea have also been reported.

15.18 Agent procurement:

Serum-derived bovine immunoglobulin protein isolate and matching placebo will be manufactured by Proliant Biologicals, Boone, Iowa in accordance with Good Manufacturing Practice (GMP) and FDA guidelines for medical good ingredients (21 CFR Part 110) and will be provided by Entera Health Inc.

15.19 Nursing Guidelines:

- 15.191 Due to the early investigational nature of this medical food, not all side effects can be known at this time. Assess for side effects and monitor patients closely.
- 15.192 Patients with beef allergy or intolerance should not take SBI.
- 15.193 GI adverse events may occur. Treat symptomatically and monitor for effectiveness.

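### Appendix II additional questions 2 and 3 have no answer between zero and once a day, and question 4 has no answer for a week without a stool

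*Combined protocol and SAP*

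**What the plan says.** Four additional questions follow the 14 PQL items in Appendix II. Three matter here.

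- **Question 2** asks "How many times per day on average did you experience nausea or vomiting". The answers are "Never 1-2 times 3-5 times > 5 times".
- **Question 3** asks "How many times per day on average did you have a bowel movement". The answers are "None 1 time 2-3 times 3-5 times > 5 times".
- **Question 4** asks "What picture represents the typical bowel movement you had over the past 7 days" and offers Bristol Types 1 to 7. No answer for the absence of a stool is printed.

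Questions 2 and 3 state no recall period; question 4 states 7 days. Section 16.63 makes the PQL items a secondary analysis, "along with the 4 additional items after the PQL questions (Appendix II) will be analyzed and compared between the 2 intervention arms". It also plans Wilcoxon rank-sum tests on changes from baseline in the QOL scores, without saying whether that covers the additional items. The primary endpoint in section 16.11 uses only the 14-item PQL total.

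**The concern.** An average per day can lie anywhere above zero, but the lowest non-zero answer on both frequency questions is once a day. Someone nauseated on three days of the week, or passing a stool every other day, has no correct answer. She must either deny the symptom or stool altogether or report it as daily. How she chooses is left to her, and with no stated recall period patients may not average over the same span of days.

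On question 4, a patient who passed no stool must leave the item blank or pick a picture that did not occur. If the change-from-baseline analysis is applied to this item, a blank at baseline removes her from every such comparison.

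The low end of the bowel scale has a safety interest. Section 15.16 states: "Literature reports indicate AEs include worsening or reoccurrence of diarrhea, constipation, and worsening neuropathy". Yet the list of events to be graded at each evaluation in section 10.6 includes diarrhea and not constipation. Under section 10.61 an unlisted event is submitted only if it is grade 2 and at least possibly related, or grade 3 or worse.

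**Working it through.** The plan gives no figure to reproduce here. The check sets possible weekly counts against the printed answers.

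**1. Frequency questions.** For k episodes in a week, the daily average is k / 7.

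| Episodes per week | Average per day | Box on question 2 | Box on question 3 | Nearest whole number |
|---|---|---|---|---|
| 0 | 0 | 'Never' | 'None' | 0 |
| 1 to 3 | 0.14 to 0.43 | no box | no box | 0 |
| 4 to 6 | 0.57 to 0.86 | no box | no box | 1 |
| 7 | 1.00 | '1-2 times' | '1 time' | 1 |

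With nearest-number rounding, 3 / 7 = 0.43 becomes zero and 4 / 7 = 0.57 becomes one. Patients who differ by one stool a week land in adjacent boxes, while three a week is pooled with none and four a week with daily. Other rounding habits move the cut, but no habit gives these patients a correct box.

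**2. Other faults in question 3.** Three a day falls in both '2-3 times' and '3-5 times'. Averages between 1 and 2 a day (8 to 13 a week) also have no box, but rounding there does not blur the difference between absent and present.

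**3. Stool chart.** Question 4 cannot be answered only if no stool was passed in all 7 days. As an illustration, assume a Poisson pattern with mean k a week, which is not in the documents. The chance of such a week is exp(-k):

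- k = 1: 37%
- k = 2: 14%
- k = 3: 5%
- k = 4: under 2%

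The problem is therefore small for most patients and concentrated in the slowest bowels. It is most likely at baseline. Sections 3.13 and 3.14 require surgery no more than 7 days before registration and resumed oral intake, but no bowel movement. This assumes that the baseline booklet is filled in around registration.

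**4. What else records the same things.**

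- *Occasional nausea:* SDS Nausea (a) has a level for nausea once in a while, PQL item 6 rates severity from 0 to 10, and nausea is graded at each evaluation (section 10.6).
- *Hard or absent stool:* question 4 Types 1 and 2, and 'None' on question 3.
- *Bowel function in general:* PQL item 8 and SDS Bowel. Both record departure from normal or discomfort without direction, so constipation and diarrhea can score alike.
- *Stool count:* section 10.6 asks for stools per day at baseline only.

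During follow-up, question 3 is the only item that measures how infrequent stools are.

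**The case against.** The best defence is that these are a few secondary items in a self-described pilot, and that the booklet measures the same symptoms in other ways. For nausea this largely stands. For bowel function it stands in part: the other scales show that something is abnormal, but not that stools are infrequent. It can also be said that weekly booklets imply a one-week recall, and that a blank on question 4 beside 'None' on question 3 can be interpreted. Both are reasonable, but neither is written down, and neither supplies the missing box.

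A reader might infer three stronger things that the documents do not support.

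- *That constipation goes unrecorded.* It does not, because Types 1 and 2 and 'None' remain.
- *That the low end of question 3 is where SBI's benefit would show.* No section says that slow bowel function is what SBI is meant to help. The human evidence in sections 1.4 and 15.11 points the other way: bowel movements falling from 5.7 to 2 a day in HIV enteropathy, fewer days of loose stools and urgency, and fewer symptoms in IBS-D. What remains at the low end is the safety interest.
- *That the gap biases the comparison or costs a known amount of power.* Assignment is double-blind with a matching placebo (sections 6.3 and 15.12), so rounding habits should not differ by arm. A power figure would need assumed proportions below once a day and a yes/no test, and section 16.63 specifies neither for these items.

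**Conclusion.** The gap is real and can be seen on the printed form. One to six episodes a week have no answer on questions 2 and 3, and a week without a stool has none on question 4. The existence of the gap rests on no assumption. Where the cut falls (three a week versus four) assumes nearest-number rounding, and the frequency of blank stool charts depends on the assumed Poisson pattern.

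The consequence is minor: less precision on two frequency items and some missing or guessed answers on a third, all secondary. No bias toward either arm is expected, and the PQL total, sample size and primary test are unaffected. It is still worth correcting, because question 3 is the only direct follow-up measure of infrequent stools, and constipation is a reported effect that section 10.6 does not solicit.

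**What to change.** In Appendix II:

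- add 'Less than once a day' between 'Never' and '1-2 times' on question 2, and between 'None' and '1 time' on question 3;
- state a 7-day recall on questions 2 and 3, to match question 4;
- add 'No bowel movement in the past 7 days' to question 4;
- in the same reprint, remove the overlap between '2-3 times' and '3-5 times' on question 3.

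In section 16.63, state that 'no bowel movement' is analysed as its own category, neither treated as missing nor given a place among Types 1 to 7. It can then be checked against 'None' on question 3.

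The cost is one reprinted page. If patients are already enrolled, answers on the old form cannot be split into the new boxes, so the form version must be recorded and the two versions kept distinguishable in the analysis.
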